## Clinical Experience

Two Phase 1 clinical studies have been completed.

A first-in-human single ascending and multiple ascending dose (SAD/MAD) study in healthy participants (GBT021601-011) has been completed. Safety and PK data on single doses up to 3000 mg in healthy participants demonstrated that osivelotor was well tolerated with a linear dose-dependent increase in percent Hb occupancy. Absorption following a single oral dose was relatively quick in plasma, with  $T_{max}$  generally ranging 0.5-3 h. Peak concentration in whole blood was achieved slower with  $T_{max}$  generally ranging 8-48 h. The terminal elimination half-life of approximately 25 to 28 days in plasma and blood was observed in healthy volunteers; however, approximately 3-fold lower terminal half-life (approximately 10 days) in plasma and whole blood was observed in SCD patients. PK exposure is generally dose-proportional and displays a high partitioning to whole blood (blood/plasma ratios of ~213 and ~68 for healthy volunteers and SCD patients, respectively, following a single 100 mg dose).

In addition, a Phase 1b Study GBT021601-012 in adult participants with SCD was conducted to evaluate the PK, safety, tolerability, and PD of single dose and MAD of osivelotor. In this open label study, a within participant dose escalation was explored. Safety, tolerability, and available PK data after each dose level were reviewed by the Safety Review Committee before escalation to the next dose level. Six adults with SCD received a single 100 mg dose of osivelotor. After an 8-week washout, participants received osivelotor loading doses of 300 mg on Day 1 and 200 mg on Day 2, followed by a maintenance dose of 50 mg/day for 5 weeks. Dose escalation occurred at Week 13 with participants receiving a 500 mg dose on Day 91, 400 mg dose on Day 92, followed by a maintenance dose of 100 mg/day for approximately 3 weeks. The study was amended to evaluate an additional maintenance dose of 150 mg/day over 6 weeks.

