## 5.3. Justification for Dose

The daily maintenance dose for adults in the open label extension study will be 150 mg, which was the optimal efficacious dose determined from Part A of C5351004. The daily maintenance dose for all adult participants who have already enrolled in C5351005 prior to this amendment may be adjusted to 150 mg.

Adolescent and pediatric participants from C5351004 Parts B and C will be administered a dose that provides generally equivalent exposure to adult participants.

Further modifications to the loading doses may be made based on cumulative data from a population PK (PPK) model. Additionally, if there are safety/tolerability issues or lack of biomarker response at higher doses in the originating study, a drug dose reduction may be instituted as noted in Section 11.3.

The methodology for loading dose selection used in this open label study will differ for participants completing Parts A, B, and C of C5351004 and are shown in Section 11.3 and Table 6. For participants from the parent study who have been off study drug treatment greater than 3 consecutive days prior to enrolling into this study, a new loading dose regimen will be initiated as shown in Section 11.3.

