**Table 6. Doses Planned Based on Participation from C5351004**

Participants from Part	Planned Dose to Initiate Treatment in Open Label Extension	Dose Adjustment
A	150 mg osivelotor	If dose is increased, a loading dose may be required. Details on the loading doses are provided in Section 11.3. The maintenance dose for all participants who have already enrolled in C5351005 prior to this amendment may be modified to 150 mg.
B	Adults: Initiate or continue with QD osivelotor 150 mg dose from Part B of C5351004. Adolescents: Initiate or continue with QD dose of osivelotor from Part B of C5351004.	Adults: Not applicable  Adolescents: Adolescent participants will be administered a dose that provides generally equivalent exposure to adult participants.
C	Continue with QD assigned dose of osivelotor from Part C of C5351004.	Treatment may be modified based on emerging data from C5351004. Adolescent and pediatric participants will be administered a dose that provides generally equivalent exposure to adult participants.

Abbreviations: QD, once daily.

Detailed information on loading dose and maintenance dose to be used based on prior participation in C5351004 can be found in Section 11.3.

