### 10.2. Analysis Sets

The analysis population for reporting are defined in the following table:

Participant Analysis Set	Description
Enrolled	All participants who sign the inform consent document and enroll in this OLE study.

Participant Analysis Set	Description
Safety Analysis Set	
All enrolled participants who have received at least one dose of study drug in this OLE study. Participants will be analyzed overall and according to the study treatment received in the parent study.
 
This analysis set will be used for all safety, efficacy, PD/biomarker, HRQOL analyses.

PK Analysis Set	All enrolled participants who receive at least one dose of study drug and have at least one concentration data point (plasma or whole blood) post dose.

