## 11.2. Supporting Documentation

### 11.3. Appendix 1: Detailed Dosing Information For Osivelotor

#### Dose for Participants Enrolling from Part A of C5351004

**Table 13. Dose for Participants Enrolled Directly from Part A of C5351004**

Maintenance Dose in Part A of C5351004	Maintenance Dose in C5351005 a
100 mg QD	Stay at 100 mg QD
	Increase to 150 mg QD
150 mg QD	Stay at 150 mg QD
	Decrease to 100 mg QD
Up to 200 mg QD	Stay at up to 200 mg QD
	Decrease to 150 mg QD
	Decrease to 100 mg QD

Abbreviations: QD, once daily.

a Until the analysis is completed from Part A of C5351004, the original dose from Part A of C5351004 should be continued in C5351005. After the optimal efficacious dose is determined in C5351004, participants may have their dose adjusted to the optimal efficacious dose in C5351005.

If there is a delay in dosing for participants from Part A of the C5351004 study prior to entry into this OLE study, a modified loading dose will be administered depending on the dose received in the previous study as follows:

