#### 4. ANALYSIS SETS (POPULATIONS FOR ANALYSIS)

Participant Analysis Set	Description	Applicable Analysis (for additional information refer to Section 6)
Enrolled	All participants who sign the informed consent document and enroll in this open-label extension (OLE) study.	Screening, Disposition, Protocol Deviations
Safety Analysis Set	All enrolled participants who have received at least one dose of study drug in this OLE study. Participants will be analyzed according to the assigned daily maintenance dose on study day 1 in the OLE study.	Demographics, Baseline characteristics, SCD History, Medical history, SCD complications history, Adverse events, Exposure, Prior and Concomitant medications, Labs, Potential Hy's Law cases, VOC, Pharmacodynamic endpoints, Weight, PROs
PK Analysis Set	All enrolled participants who receive at least one dose of study drug and have at least one measurable concentration data point (plasma or whole blood).	Whole blood and plasma concentrations

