## 5.3. General Methods

Data in general will be summarized as follows unless stated otherwise:

Participants without delayed start				Participants with delayed start				All Participants			
100 mg	150 mg	200 mg	Total	100 mg	150 mg	200 mg	Total	100 mg	150 mg	200 mg	Total

- Participants can be classified into two groups: (1) Participants without delayed start (2) Participants with delayed start.

- Participants with delayed start are those with a gap in dosing > 42 consecutive days from completing the originating study (Date of first dose in C5351005 – EOT date from parent study + 1 > 42).
- Participants without a delayed start are those with a gap in dosing ≤ 42 consecutive days from completing the originating study (Date of first dose in C5351005 – EOT date from parent study + 1 ≤ 42 days)
- Dose groups will be defined using the assigned daily maintenance dose in the C5351005 on study day 1 (SD\_1 CRF form).
- Total columns will not be presented for PK outputs.
- All figures (unless stated otherwise) will be provided for each group and all participants. In each figure, data will be presented for each dose arm and total.

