#### **Annualized rate of VOC on-treatment using Negative Binomial Model**

This analysis will not be performed by group but rather by combining all participants. A negative binomial model will be fitted to model the number of VOC events. The response variable is the number of VOC events for each participant. The independent variable is dose arm (100 mg, 150 mg) and the natural log of participant years (at participant level) will be used as the offset to account for the varying lengths of participant time on-treatment or on-study. The annualized rate and corresponding 95% CI will be presented for each dose arm and overall (100 mg + 150 mg).

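### By-dose tables keep the Day 1 dose label after a permitted dose change, which mislabels PK for anyone who switches; separately, the VOC model leaves out the 200 mg arm

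*SAP*

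**What the plan says.** **Grouping rule.** SAP 5.3: "Dose groups will be defined using the assigned daily maintenance dose in the C5351005 on study day 1". SAP section 4 applies the same rule to the Safety Analysis Set: "Participants will be analyzed according to the assigned daily maintenance dose on study day 1 in the OLE study". The general layout in SAP 5.3 has 100 mg, 150 mg, 200 mg and Total columns, but PK outputs drop the Total. SAP 6.3.6 summarizes concentrations by dose group.

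**Permitted dose changes.** Protocol 5.3: "The daily maintenance dose for all adult participants who have already enrolled in C5351005 prior to this amendment may be adjusted to 150 mg". Protocol Table 6 repeats this for Part A: "The maintenance dose for all participants who have already enrolled in C5351005 prior to this amendment may be modified to 150 mg". The Table 13 footnote first continues the Part A dose and then adds: "After the optimal efficacious dose is determined in C5351004, participants may have their dose adjusted to the optimal efficacious dose in C5351005". Protocol Table 8 lets dosing resume at a lower level after certain adverse events. SAP 2.2.3 says that only Part A participants, all adults, entered this study, so these provisions apply to the population actually enrolled.

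**VOC model.** SAP 6.2.1 says the negative binomial model pools all participants, then specifies: "The independent variable is dose arm (100 mg, 150 mg". The list stops there, and the overall rate is defined as the two arms together. The other VOC summaries in that section, including the crude annualized rate, carry no such restriction.

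**Protocol grouping.** Protocol 10.2: "Participants will be analyzed overall and according to the study treatment received in the parent study". SAP 2.1 lists four modifications to the protocol's analysis plan; the move to OLE Day 1 dose is not among them.

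**The concern.** A by-dose column is read as describing people taking that dose. Here the label is fixed at entry, while the protocol treats the entry dose as provisional for those enrolled before dose selection. The SAP itself anticipates changes, since SAP 6.1.1 tabulates adverse events leading to dose reduction, yet it has no rule for data after a change. VOC person-time runs unbroken from first dose to end of treatment (SAP 6.2.1), exposure is summarized by duration only (SAP 6.5.4), and no subset analyses are planned (SAP 6.4).

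PK has the most at stake. Its only summary is by dose arm, and concentration depends directly on the dose being taken. By-dose safety and VOC tables are affected in the same way, but they sit beside a Total column that is not.

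The VOC model raises a different problem. If anyone is in the 200 mg arm, the modelled overall rate and the crude overall rate beside it cover different people under the same name.

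**Working it through.** The plan gives no power, event count or derived sample size to reproduce on this point. It also gives no number or timing of dose changes, no VOC rates and no arm sizes. What follows is text comparison plus illustration; every share and ratio marked as assumed is mine.

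**1. PK for one switcher.** Input from Protocol 3.1: "PK exposure is generally dose-proportional". The steady-state trough relative to that expected under the label is actual dose / labelled dose:
- 100 to 150 mg: 150/100 = 1.50
- 200 to 150 mg: 150/200 = 0.75

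**2. How soon the new dose shows.** Protocol 3.1 gives a half-life of about 10 days in SCD. The fraction of the shift reached by day d is 1 - 0.5^(d/10), ignoring any loading dose:
- day 10: 50%
- day 28: 86%
- day 50: 97%
- day 84: 99.7%

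A trough 12 weeks after a change therefore reflects the new dose. One taken in the first few weeks reflects a mixture.

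**3. PK column mean.** Let D be the label and f the assumed share of the arm's samples taken at 150 mg steady state. The ratio of the column's arithmetic mean to the true mean at D is [(1 - f) x D + f x 150] / D:
- 100 mg column: f = 0.25, 0.5, 1 gives 1.125, 1.25, 1.50
- 200 mg column: f = 0.25, 0.5, 1 gives 0.94, 0.875, 0.75

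The geometric mean, which SAP 6.3.6 also reports, shifts by (150/D)^f. At f = 0.5 this is 1.22 for 100 mg and 0.87 for 200 mg.

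**4. VOC by dose.** Let RR be an assumed true 150:100 rate ratio and w the assumed share of the 100 mg column's person-years actually spent at 150 mg, with no changes in the 150 mg column. The observed ratio is RR / [(1 - w) + w x RR]:
- RR = 0.80: w = 0.25, 0.5, 0.75 gives 0.84, 0.89, 0.94
- RR = 0.60: w = 0.25, 0.5, 0.75 gives 0.67, 0.75, 0.86

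The contrast between columns is diluted towards 1.

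**5. Omitting 200 mg.** Let s be the assumed 200 mg share of person-years and r its VOC rate relative to the other arms. The modelled overall rate divided by the all-participant rate is 1 / [(1 - s) + s x r]:
- s = 10%: r = 0.5 gives 1.05; r = 1.25 gives 0.98
- s = 33%: r = 0.5 gives 1.20; r = 1.25 gives 0.92
- r = 1 gives 1.00 for any s

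**The case against.** The case for leaving the plan alone has real weight.

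- **Dose change is a permission.** Every adjustment provision is worded as something that may happen, and Table 13 also offers staying on the Part A dose. A reader might infer that the by-dose results as a whole fail to describe their label. The documents do not support that: only post-change data from switchers are affected, and how many there are is not stated.
- **Day 1 grouping is legitimate.** It is a valid descriptive convention when labelled as such. The protocol's grouping by parent treatment is also fixed at entry, so the SAP did not introduce the freezing. For participants who began on their Part A dose the two rules coincide. No hypothesis is tested (SAP 5.2), so no inference is at risk.
- **PK will also be modelled.** Protocol 10.3.5 has population PK reported separately. That does not correct the concentration tables planned here.
- **The 200 mg omission is a different defect.** A reader might infer that it too credits events to a wrong dose. It does not: it excludes those participants or leaves their handling undefined, and it has no effect if the arm is empty.
- **Crude adverse event percentages.** A reader might also infer that these are invalid without exposure adjustment. Protocol 10.1.1 specifies absolute and relative frequency, SAP 6.1.1 also counts events, and SAP 6.5.4 gives exposure duration by arm. Exposure-adjusted rates would be a preference here.
- **Dose at onset is not a clean substitute.** Reductions can follow adverse events, and a half-life of about 10 days carries exposure past a change.

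These points narrow the concern. They do not supply a rule for concentrations after a dose change or explain the missing 200 mg arm.

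**Conclusion.** The concern holds in a limited form. As written, the SAP assigns a switcher's post-change concentrations, events and person-time to the Day 1 dose. At steady state, and assuming dose proportionality, a switcher's trough is about 1.5 times that expected under the 100 mg label, or 0.75 times under 200 mg. The column shift depends on an unknown share of post-switch samples; at an assumed one half it is +25% or -12.5%, and it is zero if nobody changed dose. Total columns are not affected.

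Separately, SAP 6.2.1 contradicts itself and the SAP 5.3 layout on 200 mg. If that arm is occupied, the modelled overall VOC rate describes a different population from the crude rate. Over the assumed range (10% to 33% of person-years, relative rate 0.5 to 1.25) it would be 0.92 to 1.20 times the all-participant rate.

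The missing SAP 2.1 entry is a documentation gap only.

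**What to change.** 1. **PK.** Summarize concentrations by the maintenance dose being taken when the sample was drawn, and flag samples taken soon after a change, given the half-life of about 10 days.
2. **VOC model.** Estimate the overall rate on the full Safety Analysis Set including 200 mg, for example with an intercept-only negative binomial model and the same offset. If 200 mg is too sparse to model as an arm, report its crude rate with an exact Poisson interval, noting that this ignores between-participant variation. If no participant is in that arm, say so.
3. **Safety and VOC tables.** Keep the Day 1 grouping, title it as Day 1 assigned dose, and add a descriptive table of time at each dose. Any table of events by dose at onset should carry a caution about changes driven by adverse events and about carry-over.
4. **SAP 2.1.** List the change from parent-study treatment to OLE Day 1 dose.

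The cost is SAP wording, programming from the dosing records and a small number of added tables. Item 1 needs a stated definition of how soon after a change a sample is flagged. No inference is affected, because the analyses are descriptive.

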### 5.3.1. Analyses for Binary and Categorical Endpoints

Descriptive statistics for binary and categorical variables will be count and percentage and will be presented in the format 'n (%)'. Unless otherwise specified, the percentage in summary tables will be calculated using number of participants in the population (header N) for each dose arm as denominator.

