### 6.3.5. Patient-Reported Outcome Endpoints

- **PROMIS SF Fatigue 13a, PROMIS SF Pain Interference 8a and PROMIS NRS Pain intensity**

Descriptive statistics (Section 5.3) of the total raw score at each visit will be provided for each PRO. Total raw scores will be derived for PROMIS SF Fatigue 13a and PROMIS SF Pain Interference 8a.

PROMIS-1a will also be summarized categorically (Section 5.3) using n (%) under the following categories: 0 = None, 1-3 = Mild, 4-6 = Moderate, 7-10 = Severe.

All questions must be answered in order to arrive at the raw total score.

- **PGI-S, PGI-S of fatigue, and PGI-S of pain**

Data collected under different forms will be summarized separately. Summaries will include categorical frequency distribution (Section 5.3) over time.

- **CGI-S**

Summaries will include categorical frequency distribution and continuous descriptive summary statistics (Section 5.3) at each visit.

“Not assessed” category will be assigned as missing for continuous descriptive summary.

- **EuroQol EQ-5D-5L**

*Summary of VAS score:* Descriptive statistics (Section 5.3) will be provided at each visit for the VAS score.

*Summary of the 5 dimensions:* For each dimension, the number and percentage of participants in each of the 5 response levels will be presented.

*Summary of EQ-5D-5L Index:* Descriptive statistics (Section 5.3) will be provided at each visit for the index value.

- **WPAI+CIQ:SCD**

- Number of participants employed, total number of hours missed from work because of problems associated with SCD, total number of hours missed from work due to other reasons and total number of hours worked will be summarized descriptively (Section 5.3) by visit.
- Descriptive summary statistics (Section 5.3) for the observed SCD work productivity score will be presented at each visit.

- Number of participants who attend classes in an academic setting, total numbers of hours missed from class/school because of problems associated with SCD, total numbers of hours actually attended class/school will be summarized descriptively (Section 5.3) by visit.
- Descriptive summary statistics (Section 5.3) for the observed SCD regular daily activity score will be presented at each visit.
- Descriptive summary statistics (Section 5.3) for the observed SCD school productivity score will be presented.

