#### 6.5.2. Study Conduct and Participant Disposition

The number of participants screened based on all participants who signed informed consent, screen failures (n (%)) with percentage based on total participants screened and reasons for screen failure (n (%)) with percentages based on total number of screen failures) will be summarized for all screened participants only.

The following summaries will be presented for disposition by dose arm and overall:

- Number (%) of participants treated

- Number (%) of participants completing treatment
- Number (%) completing study
- Number (%) of participants who discontinue study or discontinue treatment along with primary reason for discontinuation

Number (%) of participants in each analysis set will be summarized in a separate table.

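### By-visit PGI-S and CGI-S percentages use the dose-arm header N, so each is scaled down by the fraction of the arm actually assessed

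*SAP*

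**What the plan says.** SAP 5.3.1 gives the default for categorical tables: unless another rule is stated, "the percentage in summary tables will be calculated using number of participants in the population (header N) for each dose arm as denominator". For patient-reported outcomes the population is the Safety Analysis Set (SAP 4): "All enrolled participants who have received at least one dose of study drug in this OLE study". Membership does not depend on reaching a visit or completing a form.

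SAP 6.3.5 then describes four categorical summaries:

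- PGI-S, PGI-S of fatigue and PGI-S of pain: "Summaries will include categorical frequency distribution (Section 5.3) over time".
- The severity scale that the clinician completes, CGI-S, has this rule instead: "Summaries will include categorical frequency distribution and continuous descriptive summary statistics (Section 5.3) at each visit".
- Pain intensity: "PROMIS-1a will also be summarized categorically (Section 5.3) using n (%) under the following categories" (none, mild, moderate, severe).
- EQ-5D-5L dimensions: "For each dimension, the number and percentage of participants in each of the 5 response levels will be presented".

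The first three point back to Section 5.3, and the fourth names no denominator. Timing is written into the PGI-S and CGI-S sentences. For the pain categories and EQ-5D-5L levels it is only implied by the by-visit summaries of the same instruments.

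The CGI-S response Not assessed is set to missing only for the continuous summary ("category will be assigned as missing for continuous descriptive summary"). SAP 5.4 covers incomplete dates, adverse event fields, laboratory values and concentrations below quantification, but not missed questionnaire visits. Where the SAP wants a different denominator it says so, as for screen failures ("with percentage based on total participants screened").

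**The concern.** A fixed denominator suits a question asked once of everyone dosed, such as whether a participant had an adverse event. It does not suit a distribution re-measured at visits that fewer and fewer people attend. The analysis windows in SAP Appendix 1.1 run to Week 84 and then continue at 12-week steps, and anyone who has left stays in the denominator of every later table without appearing in any category.

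Two collection rules add to this. Protocol Tables 1 and 2 limit these forms to sites in regions where they are available, and SAP 3.3.5 says the PGI-S forms are collected from those who completed them in the parent study. Some participants counted in header N may therefore never contribute, even at baseline. If availability differs between dose arms, the 100, 150 and 200 mg columns would differ without any difference in health.

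What is at stake is the reading of the tables. A shift in percentages may reflect who was assessed rather than how they were, and a real shift may be hidden. CGI-S shows the conflict most clearly, because its continuous summary rests on observed n (SAP 5.3.2) while its categorical summary rests on header N.

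**Working it through.** The plan states no figure to reproduce: there is no retention or dropout assumption, and no size per dose arm.

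**Inputs.** Denominator rule from SAP 5.3.1; population from SAP 4; tables from SAP 6.3.5. Assumed: the fraction assessed, the category distribution below, and unchanged health with non-selective dropout unless stated.

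**Formula.** Let N be header N, m the number assessed at the visit and n_k the number in category k.

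- Plan: n_k/N = (n_k/m) × (m/N).
- Observed-case: n_k/m.

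The plan's percentage is the observed-case one multiplied by m/N, and the categories sum to m/N rather than 100%.

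**Step 1: unchanged health.** Assume a PGI-S distribution of 20/30/30/15/5% among those assessed, at every visit.

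| Assessed (m/N) | None | Mild | Moderate | Severe | Very severe | Sum | Moderate or worse |
|---|---|---|---|---|---|---|---|
| 100% | 20 | 30 | 30 | 15 | 5 | 100 | 50 |
| 90% | 18 | 27 | 27 | 13.5 | 4.5 | 90 | 45 |
| 80% | 16 | 24 | 24 | 12 | 4 | 80 | 40 |
| 70% | 14 | 21 | 21 | 10.5 | 3.5 | 70 | 35 |
| 50% | 10 | 15 | 15 | 7.5 | 2.5 | 50 | 25 |

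Moderate or worse falls from 50% to 25%, which looks like improvement. None falls from 20% to 10%, which looks like worsening. With m as denominator every row stays 20/30/30/15/5.

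**Step 2: hidden change.** A category displayed at a constant 20% represents 20/(m/N) of those assessed: 20/0.9 = 22.2%, 20/0.8 = 25%, 20/0.7 = 28.6% and 20/0.5 = 40%.

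**Step 3: availability against attrition.** Suppose 80% of an arm can complete the form and, independently, 80% of those remain at a later visit. A true 50% displays as 50 × 0.8 = 40% at baseline and 50 × 0.8 × 0.8 = 32% later. The ratio 32/40 = 0.8 is retention alone. Fixed availability lowers the level; attrition makes the trend.

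**Step 4: selective dropout.** Take N = 20 with counts 4/6/6/3/1. Suppose six participants from the three worst categories leave and nobody's health changes, giving 4/6/3/1/0 and m = 14. Moderate or worse was 10/20 = 50%. It becomes 4/20 = 20% under the plan and 4/14 = 28.6% on observed cases. None stays at 4/20 = 20% under the plan and rises to 4/14 = 28.6% on observed cases. Changing the denominator does not remove this bias.

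**The case against.** The strongest case on the other side is that n/N is a defined quantity, the share of treated participants recorded in that category, so it is not an incorrect figure. SAP 5.3.1 prints the count beside the percentage. If all categories are shown, a reader can add the counts and recover the observed-case percentage, and a column summing to less than 100% is itself a warning. CGI-S, the pain scale, and the EQ-5D-5L VAS and index also have continuous summaries on observed data; in SAP 6.3.5 only the PGI-S forms rely on the categorical table alone. All of these endpoints are exploratory, and SAP 5.2 rules out formal testing. These points stand and they limit the consequence. They do not justify the rule, because the reader must undo the printed percentage to obtain the distribution the table appears to show, and the SAP specifies neither the number assessed nor a not-assessed row for these tables.

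Stronger readings that a reader might infer are not supported:

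- That the rule gives a one-way false improvement. Favourable categories shrink by the same factor (Step 1).
- That every percentage must fall over time. This needs a stable distribution among those remaining; a real shift or selective dropout can hold a category level or raise it.
- That restricted site availability drives a decline. It lowers the level (Step 3).
- That by-visit presentation is written for all four instruments. It is explicit for PGI-S and CGI-S only.

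**Conclusion.** The point holds as a presentational defect in exploratory tables. Followed as written, the SAP multiplies each by-visit PGI-S and CGI-S percentage by the fraction of the dose arm assessed, and the same applies to the EQ-5D-5L levels and pain categories if they are tabulated by visit. The multiplication follows from the stated rule and needs no assumption. The size in this trial is unknown because no retention or availability figures are given; 50% shown as 40% or 25% is an illustration at 80% and 50% assessed. No primary or secondary result is affected. The correction is worth making because a stated rule creates the distortion and one sentence removes it.

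**What to change.** Add to SAP 5.3.1 or 6.3.5: for by-visit categorical summaries of patient- and clinician-rated scales, the denominator is the number of participants in the dose arm with a non-missing response at that visit, with a CGI-S response of Not assessed treated as missing. Show that number for each visit and, in a separate row, the number and percentage not assessed out of header N. State that the rule covers the EQ-5D-5L levels and pain-intensity categories and that these are presented by visit. Keep header N for the adverse event, disposition and baseline tables.

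The cost is one or two sentences and a change to table shells, with no new data. The change removes the mechanical deflation. It does not correct bias from selective dropout, which is why the not-assessed row should sit beside the percentages.
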